**Figure 12**

In the thymus, the major abnormalities in the ADA-/- mice are a block in thymocyte development with an accumulation of CD4-CD8- thymocytes. Reconstituted mice with either vector or with WT or PEG-ADA treatment show similar levels of reduction of this population (fig 13).

**Figure 13**

Importantly, all the reconstitution experiments in ADA-/- mice were undertaken with clinical grade LV.SIN.EFS.hADA vector demonstrating that the clinical grade vector has equivalent immune reconstitution potential to the current SFada clinical vector that has been used successfully in clinical trials.

### 3.4.5 Genotoxicity of the EF1 $\alpha$ S-ADA lentiviral vector

It is clear from pre-clinical and clinical trial data that there is a need to move away from the use of gammaretroviral vectors which have the potential for insertional mutagenesis to the use of vector designs which have reduced transformation potential. The EF1 $\alpha$ S-ADA lentiviral vector design is likely to be significantly less mutagenic than current gammaretroviral vectors for two major reasons:

- The use of the self-inactivating (SIN) lentiviral vector backbone
- The use of the internal EF1 $\alpha$ S promoter for transgene transcription rather than the viral LTR

#### 3.4.5.1 SIN Lentiviral vector constructs are safer than LTR intact gammaretroviral constructs

The risk of insertional mutagenesis from a SIN lentiviral vector design in general is low as determined in both *in vitro* and *in vivo* systems. One *in vitro* assay has now been developed and tested by a number of groups and is gaining recognition as the most reliable test of the transformation potential of different viral constructs. The *in vitro* immortalisation assay (IVIM)

(Modlich et al., 2006; Modlich et al., 2009) detects clonal dominance of insertional mutants which expand in initially polyclonal cultures of primary murine haematopoietic cells within two weeks after gene transfer and acquire serial replating ability, the extent of which provides a measure of clonal fitness. When different vector designs were tested in this assay the SIN lentiviral vector design shows significantly less transformation potential than current LTR intact gammaretroviral designs (Modlich et al., 2006; Modlich et al., 2009).

To test the oncogenic capacity of SIN-lentiviral vectors *in vivo*, Montini et al., utilized the tumor-prone Cdkn2a-/- mouse model (Montini et al., 2006). Haematopoietic stem cells from these mice were isolated and transduced in similar conditions with SIN LV or LTR intact gammaretroviral constructs expressing reporter genes. A vector with a similar backbone as the proposed ADA vector, but expressing a neutral eGFP reporter gene, was tested in this system and no genotoxicity was found even upon integration of ~6 copies of vector per cell. In contrast, LTR-active gammaretroviral vectors were measurably genotoxic, suggesting that the intrinsic genotoxicity of the pRRL LV (the backbone used in this study) is low.

### **3.4.5.2 The EF1 $\alpha$ S promoter is safer than the viral LTR**

Using the IVIM assay, the EF1 $\alpha$ S promoter was compared under equivalent conditions to the SFFV LTR in the context of a SIN gammaretroviral vector (Zychlinski et al., 2008). In this assay a SIN vector with the internal EF1 $\alpha$ S promoter was significantly ( $P<0.01$ ) less mutagenic than a SIN vector with the internal SFFV promoter. Under conditions that resulted in death of mock-transduced cells, the SIN vector containing an internal EF1 $\alpha$ S promoter was unable to induce sustained growth of mutants, even when the average copy number was  $>40$ . In contrast, transformed clones were always observed with the SIN vector containing the internal SFFV promoter, and with this vector, an average copy number of ~2 was sufficient to induce transformation. This indicates that the transactivating potential of the SIN vector with the EF1 $\alpha$ S promoter is at least substantially diminished. Of note, SIN vectors containing 'insulator' elements flanking the internal SFFV promoter-driven cassette showed a significantly greater degree of transforming activity than the SIN vector with the EF1 $\alpha$ S promoter (4/4 experiments;  $P<0.01$ ). Together these studies indicate that the transactivating potential of gammaretroviral vectors are substantially reduced by SIN configurations (Modlich et al., 2006), and further reduced by the utilization of EF1 $\alpha$ S internal regulatory sequences.

Further *in vivo* studies have also established the low transformation capacity of SIN vectors containing the EF1 $\alpha$ S promoter. These experiments were conducted as safety studies for a trial of gene therapy for SCID-X1 (GTAC 116) and are relevant here because of the use of the same EF1 $\alpha$ S promoter. SIN gammaretroviral constructs containing the EF1 $\alpha$ S promoter and driving expression of the IL2RG or GFP reporter transgene were evaluated in murine

transplant experiments in wild type C57/BL6 experiments. Briefly lin-ve cells from donor mice were isolated and transduced under standard conditions with vectors containing EF1 $\alpha$ S-IL2RG or EF1 $\alpha$ S-GFP or media alone (mock controls). Twenty mice were transplanted for each experimental group and were observed for a period of 10-12 months. There were 17 evaluable mice in the IL2RG group, 17 evaluable mice in the EGFP group and 18 evaluable mice in the mock group. On average, there was 60-80% engraftment in each group. The average vector copy number in peripheral blood mononuclear cells, determined by real-time PCR at 2 months post-transplant was 1.25 copies/cell for the *IL2RG* test group and 2.2 copies/cell for the EGFP control group. Two host cell derived malignancies were noted in the test *IL2RG* group. One vector-negative thymoma and an ovarian tumor were noted in the GFP vector group. Host cell derived malignancies are not unexpected in this mouse model, and the frequency is not higher than previously reported values by our group. There were no cases of vector positive donor cell derived leukemias in the *IL2RG* test group. There was one vector positive, donor cell derived T cell lymphoma noted in a C57BL/6J recipient mouse which received the EGFP control vector. These data suggest that in the context of a SIN configuration and coupled with the *IL2RG* gene, the EF1 $\alpha$ S promoter has not been associated with demonstrable tumorigenesis in wild type murine transplant experiments.

#### **3.4.5.3 Data from other similar LV constructs**

Some surrogate information can also be gained from analysis of another SIN LV vector. The EF1 $\alpha$ S-ADA lentiviral vector backbone for this study is the same as that approved in a trial of lentiviral gene therapy for Wiskott-Aldrich (WAS) syndrome (GTAC 146). The promoter and transgene for the WAS vector have been removed and replaced with the EF1 $\alpha$ S-ADA cassette but the other structural elements of the virus remain the same. The WAS vector has been tested *in vivo* in *was*null recipients with a follow up of 12 months. *was*null mice transplanted with cells transduced with the WAS vector at high or low copy number had no difference in survival or tumour formation in comparison to *was*null mice transplanted with untransduced cells from WT or *was*null mice. Tumours seen were either of non-haematopoietic origin or were derived from host cells suggesting that tumour formation was not driven by vector integration. A similar frequency of tumours was seen in control cohorts (Marangoni et al., 2009). These data suggest that this WAS SIN LV vector construct has no significantly increased risk of tumour formation compared to standard transplant experiments. The EF1 $\alpha$ S-ADA lentiviral vector is therefore likely to show similar safety to the above construct.

#### **3.4.5.4 IVIM assay to test genotoxic potential of the EF1 $\alpha$ S-ADA lentiviral vector**

We have set up the IVIM assay at our laboratory and tested the transformation ability of SFFV LTR driven vectors expressing GFP (SF91.GFP) or dsRED (SF91.dsRED) reporter genes, the current SFFV LTR clinical gammaretroviral vector used in GTAC 073 (SFada/W) and the

[figure not shown]
EF1 $\alpha$ S-ADA lentiviral vector. In consecutive experiments, cells transduced with the LTR driven gammaretroviral vectors give rise to transformed clones with replating ability whereas no transformed clones above background (or mock transduced) levels were detectable in cells transduced with the EF1 $\alpha$ S-ADA lentiviral vector (Table 2) despite equivalent or higher vector copy numbers. In this assay, the genotoxic potential of the EF1 $\alpha$ S-ADA lentiviral vector is considered to be low and significantly lower than the transformation potential of the vector currently used in clinical trials.

**Table 2: IVM data**

Vector	Replating clone number (100 cells/well)	Normalized Replating clone number (100 cells/well)	VCN per cell	Replating frequency	Replating index
Mock	9	0	0.007	0	0
	11	0	0.008	0	0
	5	0	0.000	0	0
SFada/W	17	8	4.9	0.00087	0.00018
	17	6	4.7	0.00065	0.00014
	17	7	0.9	0.00076	0.00084
SF91. dsRED	27	18	5.4	0.00208	0.00039
	33	22	4.8	0.00260	0.00054
	16	4	1.4	0.00043	0.00031
SF91.GFP	65	56	1.3	0.00875	0.00694
	24	11	1.4	0.00122	0.00089
	34	18	0.2	0.00208	0.01226
LV.SIN. EFS.hADA	3	0	5.3	0	0
	6	0	4.2	0	0
	3	0	2.7	0	0

In order to test objectively whether clones derived following transduction were viable and had significant cytokine independent proliferative capacity, clones were analysed using the WST-1 assay. The assay is based on the reduction of WST-1 by viable cells which produces a soluble formazan salt. The procedure involves initial incubation of cells with the WST-1 reagent, followed by spectrophotometric assay of coloured product.

In two experiments independent experiments, any clones derived from cells transduced with the SFada/W, SF91.GFP, EF1 $\alpha$ S-ADA LV vectors or mock transduced cells were studied further in the WST-1 assay. As seen in Fig 12, in both experiments, clones derived following SFada/W or SF91.GFP transduction showed levels of proliferation that were far higher than the baseline proliferation seen in mock transduced clones. In contrast any clones derived following EF1 $\alpha$ S-ADA LV transduction showed negligible proliferative capacity and were no greater than levels of proliferation seen in mock transduced cells.

**Figure 12:** Proliferative capacity of clones generated following transduction were tested in a WST-1 assay. Clones from SFada/W and SF91.GFP transduced cells show high levels of proliferation whereas clones from EF1aS-ADA LV transduced cells have levels of proliferation no higher than that seen in mock transduced cell clones.

### 3.4.6 Clinical grade vector is able to effectively transduce human ADA-/ CD34+ stem cells

Clinical grade LV.SIN.EFS.hADA vector was characterised for its ability to transduce CD34+ cells from ADA-/ patients. Using clinical grade reagents and a clinical protocol (see section 7.6.4) involving 18 hrs prestimulation and followed by 1 round of lentiviral transduction for 24hrs, either  $1 \times 10^8$  (~MOI 100) or  $5 \times 10^7$  (~MOI 50) viral genomes were added to  $\sim 1 \times 10^6$  CD34+ cells. As shown in table 3a, these clinically applicable transduction conditions resulted in effective CD34+ cell transduction with viral copy numbers of  $\sim 1$ – $1.3$  copies/cell. In addition there was preservation of CD34+ integrity with little change in the percentage of stem cells through the culture period from D0–D3 (table 3b).

**Table 3**

a	Test	Result	Specification
	Total cell dose	$1 \times 10^8$ : $1.78 \times 10^6$ $5 \times 10^7$ : $1.78 \times 10^6$	N/A
	Gram stain	N.D. scale up in R&D lab	No organisms seen
	Culture D1	N.D. scale up in R&D lab	No organisms seen
	Transduction efficiency (mean copies/cell)	$1 \times 10^8$ : 1.34 copy/cell $5 \times 10^7$ : 0.96 copy/cell	>0.3 copies/cell

b

Day	Culture Conditions	Total CD34+	True stem cells
D0	Untransduced	94%	55%
D3	Untransduced	89%	51%
D3	$1 \times 10^8$ Ig/ml	92%	58%
D3	$5 \times 10^7$ Ig/ml	91%	58%

These data show that using a clinically applicable protocol, the clinical grade vector generated for this study is able to show effective transduction of CD34+ cells from ADA deficient patients at levels that are acceptable for clinical use and maintain CD34+ cell integrity.

### **3.5 Continuation of PEG-ADA for 1 month after infusion of gene modified cells**

There has been considerable debate as whether PEG-ADA either blunts or improves the survival of gene modified cells. In previous clinical trials, PEG-ADA has been withdrawn prior to the infusion of gene-modified cells.

Two lines of evidence now suggest that continuation of PEG-ADA may be of benefit:

- a) In a recently published murine study (Carbonaro et al., 2012) demonstrated that the continued use of PEG-ADA for 1 month after gene modified cell infusion did not diminish immune reconstitution but in fact allowed better thymic development possibly due to its protective effect on thymic epithelium.
- b) In two ADA-patients treated off trial on a compassionate basis, we also continued PEG-ADA for 1 month after gene modified cell infusion. In both cases PEG-ADA was continued because of the clinical state of the patients and the concern that removal of enzyme may have adverse clinical consequences. In both cases we have seen engraftment of gene modified cells and emergence of naïve T cell cells at 6 and 7 months post treatment.

From this we would suggest that 1) continued PEG-ADA usage is not detrimental to gene modified cell engraftment, 2) it may promote improved thymic T cell development and 3) its continued use is clinically safer for patients.

For these reasons we intend to continue PEG-ADA for 1 month after infusion of gene modified cells.

### **3.6 Busulfan dosage**

The busulfan dosage to be used in this study differs from previous studies. In this study, weight adjusted iv busulfan dosing will be given as detailed below:

Body-weight	mg/kg/day
3 to 15kg	5.1
15 to 25kg	4.9
25 to 50kg	4.1
50 to 75kg	3.3
75 to 100kg	2.7

This allows us to use the maximum daily dosage of iv busulfan and is based on European Society for Blood and Marrow Transplantation (EBMT) guidelines for Busulfan dosing in children and a recent publication (Bartelink et al., 2012).

The reason for the change is to achieve the correct balance between level of conditioning and safety. A higher busulfan dose will allow a greater degree of myeloablation and therefore greater engraftment of gene modified cells. This dosing scheme has recently been used in two ADA-SCID patients treated off-trial on a compassionate basis and in both cases the dose (both received 5.1mg/kg) was well tolerated with no toxicities.

### 3.7 Summary and rationale for use of the EF1 $\alpha$ S-ADA lentiviral vector for gene therapy

- Gammaretroviral vector mediated gene therapy for ADA has shown impressive efficacy and safety long term in 3 international studies thus far.
- Safety has been excellent with 100% survival and no serious adverse events but concerns regarding the insertional profile of gammaretroviral vectors need to be addressed.
- Lentiviral vectors encoding the EF1 $\alpha$ S internal promoter driving human ADA show efficacy of transduction and expression that is comparable to gammaretroviral constructs *in vitro*.
- Lentiviral vectors have an insertional profile that differs from gammaretroviral constructs and show decreased potential for transformation *in vitro* and in *in vivo* tumour prone models.
- The LV.SIN.EFS.hADA vector shows decreased transformation potential in an *in vitro* model of stem cell transformation and in *in vivo* transplantation experiments the EF1 $\alpha$ S-promoter in a SIN configuration does not show transformation potential.

- The LV.SIN.EFS.hADA vector shows effective reconstitution of T cell numbers and ADA activity in a murine model of ADA-/- deficiency and is comparable to the current clinical grade SFAda gammaretroviral vector.
- The LV.SIN.EFS.hADA vector shows effective transduction of ADA-/- CD34+ cells and leads to successful engraftment in NSG xenograft experiments and is comparable to the current clinical grade SFAda gammaretroviral vector.
- A clinically applicable protocol for transduction of ADA-/- CD34+ cells leads to levels of stem cell transduction that are applicable for clinical use.
- Lentiviral vector mediated gene therapy for ADA-SCID has potential for high levels of efficacy and improved safety.

## 4 Trial Design

This is a historical controlled, non-randomised phase I/II clinical trial to assess the safety and efficacy of autologous transplantation of CD34+ cells from ADA-deficient SCID infants following human ADA cDNA transfer by the EF1 $\alpha$ S-ADA lentiviral vector with comparison of outcomes to historical control group. Subjects will receive the infusion of their autologous, transduced cells following marrow cytoreduction with busulfan.

### 4.1 Patients treated with gene therapy (on study)

- Patients will be selected on the basis of inclusion and exclusion criteria as detailed below
- A back-up harvest will be retained in case of failure of reconstitution following conditioning and re-infusion of transduced cells
- For the transduction protocol (see appendix 3 for schematics), CD34+ cells will be purified from G-CSF mobilised Peripheral Blood Stem Cell (PBSCs) recovered by leukapheresis (Plerixafor may be added to enhance mobilization), whenever possible or from bone marrow harvested under general anaesthetic. Back-up cells of  $3 \times 10^6$  CD34+ cells/kg will be stored from a single procedure if sufficient cell counts available (and if not previously stored). The remaining CD34+ cells will be taken forward for transduction. If  $< 3 \times 10^6$  CD34+ cells/kg are harvested from the back-up, the patient will be withdrawn from the study

- Patients in whom of  $<1 \times 10^6$  CD34+ cells/kg are available for transduction will not proceed to conditioning, will be withdrawn from the study and will be offered a repeat harvest in approximately. 3 months
- Patient conditioning will be initiated immediately after bone marrow or PBSC collection (busulfan iv. weight adjusted dose)
- After purification, CD34+ cells will be immediately transduced with the lentiviral vector as detailed below, then evaluated for sterility, cell count, and viability, and immediately infused into patients
- Several other tests for safety including testing for RCLs will be performed on re-infused cells and results will be recorded retrospectively
- If less than  $0.5 \times 10^6$  viable transduced CD34+ cells/kg are returned to the patient, then back-up bone marrow/PBSCs will be returned and patients will be withdrawn from the study
- PEG-ADA will be withdrawn one month (+/- 6 days) post-infusion
- If there is no bone marrow recovery by 6 weeks (ANC $<0.5 \times 10^9/L$  or platelets  $< 20 \times 10^9/L$ ) the back-up harvest will be re-infused
- Patients will be followed up on study at 1 month, 6 weeks, 3, 6, 9, 12, 18, 24, 30 and 36 months post gene therapy. Visit windows will be +/- 5 days for visits at 1 month, 6 weeks and +/- 2 weeks for visits at 3, 6, 9, 12, 18, 24, 30 and 36 months post gene therapy If after 180 days there is no evidence of the transgene in PBMCs by qPCR or there is no evidence of T cell recovery, then patients will re-start PEG-ADA and will be withdrawn from the study

PEG-ADA may be restarted at PIs discretion prior to this time point on clinical grounds e.g infective problems or delayed immune reconstitution and at this stage will be withdrawn from the study.

[figure not shown]
#### **4.2 Patients treated with gene therapy (off study): CUP group**

In addition to the patient treated on trial, another sub-group of patients treated on compassionate basis (CUP) with the same gene therapy under GOSH License, that followed the procedure of this protocol are included within this protocol and will be part of the analysis (see section 8.9). Details about this group of patient can be found in Appendix 9.

#### **4.3 Historical control group: HSCT group**

Historical HSCT data from a database of ADA-SCID patients treated with allogeneic HSCT from GOSH will be collected as comparator group and considered for the analyses (see section 8.9). Details about this group of patient can be found in Appendix 9.

## Trial summary

## 4.2 Trial objectives

### 4.2.1 Primary objectives

The primary objective is to assess the safety and efficacy of EFS-ADA LV mediated gene therapy, the Investigational Medicine Product (IMP) for treatment of ADA-SCID patients. This will be achieved via the following specific objectives:

#### Safety

1. To assess clinical, haematological and immunological progress of patients
2. To assess vector integration sites and clonal proliferation. This analysis will be performed at a specialised laboratory in Germany and the data will be reviewed and interpreted by the PI and the study team

#### Efficacy

1. To assess overall survival (OS) at 1 year for patients treated with IMP
2. To assess event free survival (EFS, defined below in Section 5.2.2) at 1 year for patients treated with IMP
  - o To compare OS and EFS at 1 year between patients treated with IMP and patients treated with allogeneic HSCT
3. To assess at each visit engraftment success and resulting immunological and metabolic effects in IMP treated patients using:

- a. Vector copy numbers in peripheral blood leukocytes
- b. Cellular and humoral immune system recovery
- c. ADA activity and reduction in dATP in peripheral blood cells

#### **4.2.2 Secondary objectives**

The secondary objectives are to:

- Compare survival and event free survival at 2 and 3 years between patients treated with IMP and patients treated with allogeneic HSCT
- Determine the percentage of IMP treated patients requiring immunoglobulin replacement therapy at all evaluation points from 18 months onwards
- Compare frequency of infections, and growth of pathogenic microorganisms over 3 years
- Evaluate the longitudinal clinical effect in terms of improved immunity
- Evaluate tolerability of conditioning regimen. These data will be reviewed and interpreted by the PI and the study team
- Evaluate feasibility of the transduction procedure. These data will be reviewed and interpreted by the PI and the study team

### **4.3 Study endpoints**

#### **4.3.1 Primary endpoints**

- To assess survival at 1 year for patients treated with IMP.
- To assess event free survival at 1 year for patients treated with IMP.
  - To compare survival and event free survival at 1 year for patients treated with IMP compared to patients treated with allogeneic HSCT.
- Success of engraftment of transduced cells as assessed by vector copy number in the cells at each study visit.
- Reconstitution of cell mediated and humoral immunity as assessed by evidence of changes in T cell number, function and circulating immunoglobulin levels at each study visit.
- Correction of metabolic abnormalities as assessed by dATP and evidence of ADA activity in erythrocytes at each study visit compared to published data from HSCT treated patients

The following will be analysed at a specialist laboratory in Germany and the results reviewed and interpreted by the PI and the study team.

- Analysis of frequency of vector integration into known proto oncogenes
- Analysis of frequency of clonal expansion associated with vector integration near proto oncogene

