### **8.4 Withdrawal of individual subjects**

A patient can withdraw or be withdrawn from protocol treatment in the study at any time from enrolment until the transduced CD34+ cells have been administered. Once a patient has been administered the transduced CD34+ cells study treatment is complete.

- Patients from whom  $<3 \times 10^6$  CD34+ cells/kg are harvested for the back-up, will be withdrawn from the study prior to conditioning and offered a repeat harvest
- Patients from whom  $<1 \times 10^6$  CD34+ cells/kg are harvested for transduction, will be withdrawn from the study prior to conditioning and offered a repeat harvest
- If less than  $0.5 \times 10^6$  viable transduced CD34 + cells/kg are returned to the patient, then back-up bone marrow/PBSCs will be returned and patients will be withdrawn from the study
- If after 180 days there is no evidence of the transgene in PBMCs by qPCR or there is no evidence of T cell recovery, then patients will re-start PEG-ADA and will be withdrawn from the study

PEG-ADA may be restarted at PIs discretion prior to this time point on clinical grounds e.g infective problems or delayed immune reconstitution and at this stage will be withdrawn from the study. The decision for patients to remain off PEG-ADA is dependent on a combination of factors including:

- 1) metabolic detoxification as assessed by sustained red blood cell dATP levels  $<250$  umol/l
- 2) T cell recovery as assessed by absolute T cell numbers (CD3+ cells)  $>300$  cells/mm^3
- 3) engraftment of gene modified cells as assessed by vector copy number in CD3+ cells  $>0.05$  ( $>5\%$  of total T cells)

Subjects who wish to discontinue from the study at any time are free to do so. However the reasons for discontinuation should be documented by the investigator if possible.

Patients who withdraw from the study after administration of the transduced CD34+ cells for reasons other than those given above will be encouraged to have follow-up investigations so that the consequences of the administration can be documented and analysed.

Any patient withdrawn prior to administration of transduced CD34+ cells will be replaced in the study.

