#### Efficacy

- To assess overall survival and event-free survival at 1 year for subjects treated with IMP and compare with patients treated with allogeneic HSCT
- To assess at each visit engraftment success and resulting immunological and metabolic effects in IMP treated subjects using:
  - Vector copy numbers in peripheral blood leukocytes
  - Cellular and humoral immune system recovery
  - ADA enzyme activity and reduction in dATP in peripheral blood cells

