## 5 Endpoints

### 5.1 Primary Endpoints

Primary endpoints for this study are:

- Overall survival at 1 year for patients treated with IMP.
- Event-free survival at 1 year for patients treated with IMP.

- Vector copy number in the cells at each study visit.
- Changes in T cell number, function and circulating immunoglobulin levels at each study visit.
- dATP and ADA enzyme activity in erythrocytes at each study visit.

The following endpoints will be analysed at a specialist laboratory in Germany and the results will be reviewed and interpreted by the PI and the study team, so these will not be included in this Statistical Analysis Plan (SAP).

- Frequency of vector integration into known proto oncogenes.
- Frequency of clonal expansion associated with vector integration near proto oncogene.

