### **8.3.1.3 Engraftment**

Engraftment of transduced cells will be assessed using vector gene marking in granulocytes, PBMC, CD3, CD34, CD19 and myeloid progenitor cells. Any assessments in which the result indicates that cells were not detected, will be assigned a value of 0.

The vector copy numbers in each type of cell will be summarised for IMP treated subjects by visit using descriptive statistics. In addition, for each cell type, plots of the median and range for copy numbers over time on a logarithmic scale will be produced along with individual subject plots.

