### **8.3.1.5 RBC ADA Enzyme Activity and Reduction in dATP**

RBC ADA enzyme activity, dATP and plasma deoxyadenosine will be summarized by visit for each of the IMP treated groups using descriptive statistics. The median value and range will be plotted by treatment group over time on a logarithmic scale. In addition, individual subject plots will be created.

Changes from baseline in each of the parameters will be calculated with baseline being the pre-treatment evaluation. The change from baseline will be summarized by visit for each of the IMP treated and HSCT control groups (data permitting) using descriptive statistics and 95% confidence intervals.

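### Engraftment success, immune reconstitution and metabolic correction are primary, but the SAP plans no pre-specified number (%) of infused children reaching any level, and later by-visit summaries can omit the children who failed

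*Protocol*

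**What the plan says.** Protocol 4.3.1 lists three biological primary endpoints beside survival:

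- The engraftment endpoint is worded as a success: "Success of engraftment of transduced cells as assessed by vector copy number in the cells at each study visit".
- The immunity endpoint, which comes next in the list, is worded as a recovery: "Reconstitution of cell mediated and humoral immunity as assessed by evidence of changes in T cell number, function and circulating immunoglobulin levels".
- The metabolic endpoint, last of the three, is worded as a return to order: "Correction of metabolic abnormalities as assessed by dATP and evidence of ADA activity in erythrocytes at each study visit compared to published data".

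SAP 4.1 keeps the idea of success in the primary efficacy objective: "To assess at each visit engraftment success and resulting immunological and metabolic effects in IMP treated subjects using". SAP 5.1 then restates the endpoints as measurements, for example "Vector copy number in the cells at each study visit".

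The planned analyses differ by endpoint:

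- **Engraftment (SAP 8.3.1.3):** "The vector copy numbers in each type of cell will be summarised for IMP treated subjects by visit using descriptive statistics", with median and range plots and individual plots.
- **Lymphocyte subsets (SAP 8.3.1.4):** by-visit summaries, a paired t or Wilcoxon test of change at 6 and 12 months, a mixed model for trend, and individual plots against age-dependent normal ranges.
- **ADA activity, dATP and deoxyadenosine (SAP 8.3.1.5):** by-visit summaries and individual plots, "The median value and range will be plotted by treatment group over time on a logarithmic scale", and change from baseline with 95% CIs.

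Protocol 8.4 attaches numbers to the same variables when listing what informs the decision to stay off PEG-ADA. One item is "metabolic detoxification as assessed by sustained red blood cell dATP levels" below 250 umol/l. The others are CD3+ cells above 300/mm3 and CD3+ vector copy number above 0.05. The SAP does not use any of these levels.

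**The concern.** A primary endpoint worded as success, reconstitution or correction leads a reader to ask how many of the treated children achieved it. The three SAP sections describe averages, spread, change and trend instead. If the report gives a success count, its cut-off and denominator will have been chosen after open-label data were seen.

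The denominator matters as much as the cut-off. The children who fail biologically are the ones the protocol withdraws and puts back on enzyme. Later by-visit summaries may describe mainly the children who did well.

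**Working it through.** The documents give no sample-size calculation or expected response rate, so there is no planned figure to reproduce. The check sets the texts side by side and then asks how precise the missing estimate would be.

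**1. Endpoint against analysis**

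| Primary endpoint | SAP analysis | Level already in the protocol | Number (%) at a level |
|---|---|---|---|
| Engraftment | 8.3.1.3: descriptive, plots | 8.4: CD3+ vector copy number >0.05; 8.3: failure if <0.1% at 6 months | None |
| Immunity (cell counts) | 8.3.1.4: descriptive, paired tests, mixed model, plots with normal ranges | 8.4: CD3+ >300 cells/mm3 | None |
| Metabolic | 8.3.1.5: descriptive, change with 95% CI, plots | 8.4: sustained dATP <250 umol/l | None |

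**2. What is counted per child elsewhere**

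- Event-free survival (SAP 8.3.1.2): death, return to PEG-ADA, or second transplant.
- PHA and CD3 stimulation categories (8.3.3.3, 8.3.3.4).
- Tetanus response (8.3.3.7).
- Stopping immunoglobulin replacement, with exact CIs (8.3.2.2).

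These cover T-cell function, humoral recovery and clinical failure. None counts children by vector copy number, CD3+ count or dATP.

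**3. Does the tabulated summary fix the count?** No. Take two invented sets of 10 vector copy numbers:

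- A: 0.01, 0.02, 0.03, 0.04, 0.5, 0.7, 0.8, 0.9, 1.0, 2.0
- B: 0.01, 0.06, 0.3, 0.4, 0.5, 0.7, 0.8, 0.9, 1.0, 2.0

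Both have median (0.5 + 0.7)/2 = 0.6 and range 0.01 to 2.0. The means are close: 6.00/10 = 0.60 and 6.67/10 = 0.667. Yet 6/10 in A and 9/10 in B exceed 0.05. This shows only that the summary does not determine the count. It does not predict the trial's data.

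**4. Who is in the later summaries?**

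- Protocol 4.1 and 8.4: a child with no transgene or no T-cell recovery after 180 days restarts PEG-ADA and is withdrawn.
- Protocol 8.4: follow-up after infusion is encouraged for children who withdraw for reasons other than those listed, so it is unclear whether data on listed failures continue.
- SAP 8.3.1.3 to 8.3.1.5 have no rule for these children.
- Protocol 3.2.2: circulating enzyme can bring metabolite levels to normal in deficient cells.

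If data stop at withdrawal, later medians exclude the failures. If data continue, a low dATP may reflect the enzyme rather than the gene therapy.

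**5. Precision of the missing proportion.** The Clopper-Pearson 95% limits for x of n are the 2.5% point of Beta(x, n−x+1) and the 97.5% point of Beta(x+1, n−x). With n = 10 (SAP 7.1) and x assumed:

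- 8/10: 44.4% to 97.5%
- 10/10: lower limit 0.025^(1/10) = 0.692, so 69.2% to 100%

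**The case against.** The strongest reply is that these endpoints were never meant as responder rates. The immunity endpoint is worded in terms of change, the metabolic one as a comparison with published data, and Protocol 8.1.1 says immunological results are to be read longitudinally for each patient. SAP 5.1 lists continuous measures and the analyses match them. Splitting 10 continuous profiles at a cut-off loses information, and the intervals are wide.

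The reply also notes that failure already reaches a primary per-child estimate. Failure after 180 days triggers PEG-ADA, which is an event in the event-free survival analysis. Individual plots are planned for all three measures, so with 10 children a reader can count. Finally, the 8.4 levels inform a treatment decision alongside other factors and do not define success. Protocol 3.2.2.1 describes enzyme-treated patients with 12 to 500 T cells/mm3 as all below normal, so 300/mm3 is not a normal value.

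Much of this stands. The continuous analyses should stay, the count should be supportive, and the 8.4 levels must be labelled as analysis cut-offs. Two things are left unanswered. A count read off plots has no pre-specified cut-off or denominator. Event-free survival does not show which biological level was reached: staying off PEG-ADA is decided on several factors together, so an event-free child can still miss one of them.

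**Conclusion.** The gap is real but limited. For three primary endpoints, the SAP gives no pre-specified number (%) of infused children reaching a level, and no rule for children withdrawn after failure. Overall and event-free survival are unaffected.

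Three stronger readings are not supported:

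- **That the plan offers only descriptive statistics and plots for all three.** This is true of engraftment alone; lymphocyte subsets have tests and a model, and metabolic change has CIs.
- **That the plan cannot show how many children succeeded.** The individual plots and the related counts allow a partial answer after the fact.
- **That a good median would usually hide failures at some calculable rate.** Any such figure mostly restates the failure rate assumed. At an assumed 30%, two or more failures in 10 occur with probability 1 − 0.7^10 − 10 × 0.3 × 0.7^9 = 0.85, whatever the median shows. The documents give no rate.

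The only size that can be stated is the precision: with n = 10 the proportions will be imprecise, as the intervals above show. How far later summaries would shift depends on how many children fail and whether their data continue, and the documents settle neither.

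**What to change.** Keep every planned analysis. Add one supportive table to SAP 8.3.1.3 to 8.3.1.5, for each IMP group, at months 6 and 12 and at later scheduled assays (the nearest scheduled assay where a variable is not measured at that month). Give the number (%) of all infused children, with exact 95% CI, meeting:

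1. CD3+ vector copy number >0.05
2. CD3+ >300 cells/mm3
3. sustained red-cell dATP <250 umol/l
4. all three

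State these rules in the SAP:

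- The denominator is all infused children. Death, withdrawal for failure or return to PEG-ADA counts as not met.
- The levels are analysis cut-offs taken from Protocol 8.4. They are neither normal values nor care rules, and no care rule changes.
- The dATP criterion keeps its requirement to be sustained, and the SAP says how that is applied across visits.
- The SAP explains how the 0.05 level relates to the <0.1% figure in Protocol 8.3, which defines engraftment failure and serves a different purpose.

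The data are already collected and the SAP already uses exact intervals, so the cost is some wording and a few table rows. The percentages will be imprecise, may look less favourable than the medians, and will partly overlap with event-free survival.
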